#  Visit 4 - Day 3 – 48 hours

- Furosemide infusion to continue if clinically indicated
  - If patient deemed to not require standard of care by day 3 and has their diuretic treatment de-escalated efforts will be made to replace patient. All data collected will be retained but patient will be deemed to have completed the study and further studyrelated investigations not carried out.
- Body weight, blood pressure and heart rate measured by nursing staff
- Bloods taken
  - o Urea and electrolytes
  - o Full blood count
- Acetazolamide 250mg to be given by ward staff in the morning (48 hours after first dose) and 6 hours later (in ACZ group only) as per electronic prescription
- Ongoing input from treating team: ward round and any input that stems from that, regular observations from nursing staff, input from other health professionals if indicated (for example dieticians, physiotherapists, occupational therapists)
- Study doctor visit (48 hours +/- 2 hours from first dose of ACZ (ACZ arm) or randomisation (SoC arm)

- Clinical examination and medical history
- Diet sheet collected from previous day
- Fluid balance and urine output
- Patient assessed breathlessness using 5-point Likert breathlessness scale
- Urine collection to stop at 48 hours after first dose of ACZ or randomisation
- Patient provided with 24hr urine electrolyte bottle if not catheterised and instructed to begin collection at 72hrs from the first dose of acetazolamide the following day
  - Nursing staff to be informed

# Visit 5 - Day 4 – 72 hours

- Furosemide infusion to continue if clinically indicated
  - If patient deemed to not require standard of care by day 4 and has their diuretic treatment de-escalated the patient will be deemed to have completed the study and further study-related investigations not carried out.
  - Body weight, blood pressure and heart rate measured by nursing staff
- Bloods taken

.

- o Urea and electrolytes
- o Full blood count
- Acetazolamide 250mg to be given by ward staff in the morning (72 hours after first dose) and 6 hours later (in ACZ group only) as per electronic prescription
- Ongoing input from treating team: ward round and any input that stems from that, regular observations from nursing staff, input from other health professionals if indicated (for example dieticians, physiotherapists, occupational therapists)
- Study doctor visit (72 hours +/- 2 hours from first dose of ACZ (ACZ arm) or randomisation (SoC arm)
  - o Clinical examination and medical history
  - Diet sheet collected from previous day
  - o Fluid balance and urine output
  - o 24 hour urine collection to begin 72 hours from first dose of ACZ or randomisation
    - Patient asked to empty bladder or nursing staff to empty catheter bag and then begin urine collection
  - Patient assessed breathlessness using 5-point Likert breathlessness scale

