# 3.4 **Primary endpoint/outcome**

Difference in mean net fluid loss daily and over a 4 day period

• Total volume intake in millilitres (mL) – total volume passed as urine in mL

Difference in serum chloride concentrations between day 1 and day 4

• Serum chloride day 4 – serum chloride day 1

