#  Visit 3 - Day 2 – 24 hours

- Furosemide infusion to continue if clinically indicated
  - If patient deemed to not require standard of care by day 2 and has their diuretic treatment de-escalated efforts will be made to replace patient. All data collected will be retained but patient will have "completed" the study early.
- Vital signs measured by nursing staff
- Bloods taken
  - Urea and electrolytes
  - o Full blood count
- Acetazolamide 250mg to be given by ward staff in the morning (24 hours after first dose) and 6 hours later (in ACZ group only) as per electronic prescription
- Ongoing input from treating team: ward round and any input that stems from that, regular observations from nursing staff, input from other health professionals if indicated (for example dieticians, physiotherapists, occupational therapists)
- Study doctor visit (24 hours +/- 2 hours from first dose of ACZ (ACZ arm) or randomisation (SoC arm)
  - Clinical examination and medical history
  - o Diet sheet collected from previous day
  - Fluid balance and urine output
  - o 24 hour urine collection to begin 24 hours from first dose of ACZ or randomisation
    - Patient asked to empty bladder or nursing staff to empty catheter bag and then begin urine collection
  - o Patient assessed breathlessness using 5-point Likert breathlessness scale

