#### 7.9 Withdrawal criteria

Patients can be withdrawn from the trial if:

- They withdraw their consent at any point during the study **for any reason**. This can happen at any time after consent and during follow up. In such an event no additional data will be collected from the patient and there will be no follow up. The study doctor will ascertain whether the patient wishes the withdrawal of consent to apply retrospectively to the withdrawal (i.e. can we use data already collected?). The outcome of any and all discussions regarding the withdrawal of consent will be documented in the medical notes and case report form.
- A patient's condition deteriorates due to heart failure or another pathology to the extent that they are expected to die within the next 24 to 48 hours.
- The study doctors deems the risk of continuation due to serious drug reactions or adverse events is too great to the patient. This will be fully discussed with the patient and the content and outcome of all discussions will be documented in the medical notes and CRF.
  - Worsening symptoms of heart failure\*
  - Hyponatraemia (<135 mmol/L)
    - Asymptomatic\*
      - Severe (<130 mmol/L)\*

    - Symptomatic (confusion, drowsiness, nausea or vomiting)\*\*
  - Hypotension
    - Asymptomatic\*
    - Symptomatic with no sequelae\*
    - Symptomatic with significant sequelae i.e. fall due to postural hypotension\*\*
  - o Hyperchloraemia
    - Mild 107 110 mmol/L\*
    - Severe >110mmol/L\*\*
  - Worsening renal function
    - >30% increase in serum creatinine from admission. \*
    - >50% increase in serum creatinine from admission.\*
    - >100% increase in serum creatinine from admission.\*\*
  - Side effects of acetazolamide: haemorrhage, ataxia, depression, diarrhoea, dizziness, fatigue, flushing, irritability, headache, loss of appetite, nausea, vomiting, taste disturbance, paraesthesia,
    - Tolerable to the patient.\*
    - Intolerable to the patient.\*\*

\* - Clinically relevant safety endpoint that would not automatically lead to the discontinuation of the study drug. Withdrawal would be at patient's request or the study doctor's discretion if the risk of continuation was deemed too high.

\*\* - Occurrence would lead to withdrawal from the study if it occurred in the acetazolamide arm

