We will attempt to replace patients that withdraw from the trial prior to completing day 4 assessments. The reason(s) for withdrawal will be carefully monitored for trends in patient opinions of participation in the study, adverse drug reactions or adverse events.

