# Net fluid loss

Current guidelines recommend a target of ~1000ml net fluid loss per day during in-patient diuresis, which generally occurs over a period of up to 9 days (median length of stay for a patient hospitalised with heart failure in the UK). We estimate that a clinically significant difference in daily net fluid loss is 500-1000 ml – a minimum of 4.5L over a 9 day period and 2L over the 4 day period of our study. Such an increase in net fluid loss would indicate a significant increase in diuresis that may shorten hospital admission.

Using the available data on urine output (appendix 7), we expect an average daily fluid loss of 1000ml per day with a standard deviation ranging from 500-1000ml. Patients admitted with heart failure are often breathless on very modest exertion thus we anticipate a drop-out rate of 10% in the control arm. Furthermore, given the lack of reliable clinical data on the tolerability of acetazolamide we have anticipated a higher drop-out rate of 20% in the acetazolamide arm. Thus, to detect a difference of

500-1000ml in net fluid loss per day with statistical power of 80% and two-tailed significance of 5% we would need to recruit a minimum of 35 patients (17 in the control arm and 18 in the acetazolamide arm).

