# 10.7 Procedure(s) to account for missing or spurious data

We will attempt to replace any patient with data missing for either primary endpoint (i.e. those who did not complete 4 days of treatment, those with data on net fluid loss missing on any day, and those with data on serum chloride missing on baseline or day 4). However, we expect missing data to be a minor problem as data collection for net fluid loss will be done by the study team during each visit and data on chloride concentrations will be collected as part of routine care. Reasons for missing data will be recorded in a dedicated section within the CRF for each study visit. We will not perform any imputation of missing data.

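### Patients whose diuretic is de-escalated early, or who have certain events in the acetazolamide arm only, drop out of the primary data, so the 4-day comparison rests on patients selected after randomisation

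*Protocol*

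**What the plan says.** The co-primary endpoints (Protocol 3.4) are "Difference in mean net fluid loss daily and over a 4 day period" and "Serum chloride day 4 – serum chloride day 1".

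**De-escalation (7.7 footnote and 7.8).** If a patient is judged not to need standard of care by day 2 and "has their diuretic treatment de-escalated efforts will be made to replace patient", the patient counts as having completed early. The Visit 4 text also provides for replacement and adds that study investigations stop. At Visit 5, "the patient will be deemed to have completed the study and further study-related investigations not carried out"; replacement is not mentioned there. Visits 3 and 4 say that data already collected are kept.

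**Arm-specific withdrawal (7.9).** The double-asterisk events are symptomatic hyponatraemia, hypotension with significant sequelae, chloride above 110 mmol/L, creatinine up by more than 100%, and intolerable side effects. Of these: "Occurrence would lead to withdrawal from the study if it occurred in the acetazolamide arm". Then: "We will attempt to replace patients that withdraw from the trial prior to completing day 4 assessments".

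**Analysis.**
- 10.7: "We will attempt to replace any patient with data missing for either primary endpoint". This covers anyone without 4 days of treatment or with any day of fluid data missing. Nothing is imputed.
- 10.3.2 excludes patients with missing co-primary data.
- 10.1 and 10.3.2 remove patients with under 20 hours of furosemide, or more than 5 g of salt, in a day.
- 10.6 applies the intention-to-treat analysis to patients who complete the study.

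**The concern.** Section 7.7 defines clinical euvolaemia as absence of venous congestion or a move to oral diuretic. De-escalation is therefore closely tied to what the fluid endpoint measures. If acetazolamide works, more of its patients should reach that point early, and the patients left with a 4-day total in that arm would be its slower responders. Replacement refills the count with patients who are kept only if they, too, do not stop early, so it does not restore the randomised comparison. The withdrawal rule adds a selection that operates in one arm only. The trial is open label (7.4), so the decision to de-escalate could itself depend on the arm.

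This matters even in a pilot. Section 4 describes the study as powered for superiority on both primary endpoints, and Section 2 says the results will be used to design a large multicentre trial.

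**Working it through.** **1. What remains for a de-escalated patient (7.7, 7.8).**

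| De-escalated at | Fluid data in hand | 4-day total | Scheduled 72-h chloride | Replacement |
|---|---|---|---|---|
| Visit 3 (24 h) | day 1 | none | after stopping | stated |
| Visit 4 (48 h) | days 1–2 | none | after stopping | stated |
| Visit 5 (72 h) | days 1–3 | none | can exist: bloods are listed at that visit | only through 10.7 |

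Visit 3 says the patient has completed early without saying that measurement stops; I read it in line with Visits 4 and 5. The first days survive for the daily comparison. The 4-day fluid total is lost in every row.

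**2. Whether the analysis rules recover these patients.** They do not. Without imputation there is no 4-day total. The under-20-hour rule is explained by lost IV access but, as worded, also catches a patient whose infusion was stopped on clinical grounds. Section 10.1 lists such removals separately from the per-protocol analysis, so they are not confined to it. The 10.6 set is ambiguous, because 7.8 labels these patients as having completed. Even if they are counted in, they have no 4-day value.

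**3. The plan's own allowance for loss.** Section 10.1 assumes drop-out of 10% (control) and 20% (acetazolamide). With the difference equal to one SD, n per arm = 2 × (1.96 + 0.84)² / 1² = 15.7. Then 15.7 × 1.1 = 17.3 and 15.7 × 1.2 = 18.8, which truncate to the stated 17 and 18. The allowance is justified by breathlessness and tolerability, not early decongestion, and it restores numbers only.

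**4. Direction for fluid loss.** Simulation, 400,000 patients per arm. From 10.1: "we expect an average daily fluid loss of 1000ml per day with a standard deviation ranging from 500-1000ml", and a true effect of 500 or 1000 mL/day. My assumption: de-escalation once cumulative loss reaches 4, 5, 6 or 7 L by 72 h. Losses are 0.1–37% of controls and 2–95% of the acetazolamide arm, always more in the latter. The completer difference is 31–96% of the difference with everyone left on the infusion, and below it in every scenario.

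**5. Why this does not give a size.** Second model: daily loss = 1633 mL (high-dose arm of the loop-diuretic dosing trial, Appendix 2) + 500 mL on acetazolamide + patient and day components, each with SD 1000 mL (assumed). De-escalation follows a sharp threshold on 48-h loss. With nobody's loss altered, the 4-day difference is 4 × 500 = 2000 mL. The last column lets loss after de-escalation fall to between 0 and 50% of its undisturbed value (assumed).

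| Controls leaving | Acetazolamide leaving | Completer difference (mL) | All-randomised difference (mL) |
|---|---|---|---|
| 10% | 19% | 1429 | 1359–1688 |
| 20% | 33% | 1212 | 1103–1559 |
| 30% | 46% | 1069 | 967–1492 |

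The completer figure lies inside the all-randomised range in each row. If the trigger correlates only 0.5 with 48-h loss, the completer difference is 1776–1882 mL, which is 6–11% below 2000 mL.

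**6. The chloride trigger.** Appendix 2 gives admission chloride of 100 mmol/L, SD 3, in patients with normal admission values. At mean 100, the proportion above 110 is 1 − Φ(10/3) = 0.04%. At mean 103.6 (100 plus the whole 3.6 mmol/L target), z = 6.4/3 = 2.13 and the proportion is 1.6%. Removing that tail lowers the mean by 3 × φ(2.13)/Φ(2.13), about 0.13 mmol/L.

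**The case against.** Four points on the other side deserve weight.

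- **Size.** A reader might set the completer figures above against 2000 mL and conclude that the effect would be understated by 29–47%. The documents do not support that. The 2000 mL benchmark supposes that loss is unchanged after the infusion is reduced, and no de-escalation rate is given. Patients enter with severe congestion, and 4 days is about half the median stay (2.1), so early de-escalation may be uncommon. This objection stands.
- **Tolerability.** A reader might infer that the worst tolerability outcomes vanish from one arm. They do not. All adverse events and reactions are recorded (9.2), collected to discharge (9.5) and followed to resolution or 30 days (9.11). Adverse events and drop-out are analysed (10.3.3). Section 7.9 rules out further data only when consent is withdrawn.
- **Chloride.** A reader might take all day-4 chloride to be lost. A patient stopped at Visit 5 can already have the 72-h sample, and routine biochemistry may supply others. The trigger above 110 mmol/L looks minor.
- **Meaning of de-escalation.** The text says only that standard of care is no longer needed. Response is the likely reason, not the only possible one, so the direction of bias is probable rather than certain.

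None of this restores a 4-day fluid total for de-escalated patients, or removes the difference between arms in the withdrawal rule.

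**Conclusion.** The point holds as a design flaw. Followed as written, the protocol drops patients from the 4-day fluid comparison because of a post-randomisation event likely to be related to response, and applies one withdrawal rule to the acetazolamide arm alone. Chloride is affected for patients stopped before the 72-h sample, or removed by the furosemide-hours rule even where a sample exists. For fluid loss the probable direction is towards no effect, provided de-escalation mostly reflects decongestion and acetazolamide increases diuresis. No percentage can be attached to it from the documents. The case for change rests on keeping the randomised groups comparable, not on a simulated shortfall. It should be settled by amendment, because measurements not taken cannot be recovered later.

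**What to change.** Leave clinical decisions on de-escalation and on stopping tablets to the existing rules, but separate them from stopping data collection.

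1. In 7.7–7.9: for every randomised, consenting patient still in hospital, in both arms alike, keep recording fluid balance and weight to 96 h and serum chloride to the scheduled day-4 sample.
2. The sponsor should reconcile the arm-specific withdrawal wording in 7.9 with that common collection rule.
3. In 10.6: define the intention-to-treat set as all randomised patients with available data, in their allocated arm.
4. In 10.1 and 10.3.2: confine the under-20-hour furosemide and over-5 g salt removals to the per-protocol analysis. Without this and item 3, the same patients would still be discarded.
5. In 7.7, 7.8, 7.9 and 10.7: delete replacement for de-escalation and for double-asterisk events.
6. Report early de-escalation and early discharge by arm alongside time to euvolaemia, and state how the 4-day total is handled after discharge.

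Cost: amendment wording and some extra data entry. Weight and urine output are daily routine care (7.8), but routine biochemistry there is promised only at least every 48 hours, so an occasional extra sample may be needed. The estimate also changes meaning: it becomes the effect of a treatment strategy that includes de-escalation, which may be smaller than the effect with everyone kept on the infusion.

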#### Visit 6 - Day 5 – 96 hours

- Ongoing input from treating team: ward round and any input that stems from that, regular observations from nursing staff, input from other health professionals if indicated (for example dieticians, physiotherapists, occupational therapists)
- Study doctor visit (96 hours +/- 2 hours from first dose of ACZ (ACZ arm) or randomisation (SoC arm)
  - Clinical examination and medical history
  - Diet sheet collected from previous day
  - Fluid balance and urine output
  - Patient assessed breathlessness using 5-point Likert breathlessness scale
  - Urine collection to stop at 96 hours after first dose of ACZ or randomisation
  - Ultrasound assessment of congestion
    - IVC diameter

# Visit 7 - 30 day Telephone Follow Up (from point of randomisation)

- Discuss any concerns or queries regarding the trial and treatment
- Invite participants to any and all presentations of the data at local or national events
- Outcome data from electronic records (from point of baseline visit)

• Any hospitalisations or death

#### Visit 8 - 180 day Follow up (from point of baseline visit)

- Outcome data from electronic records
- Any hospitalisations or death

#### 7.9 Withdrawal criteria

Patients can be withdrawn from the trial if:

- They withdraw their consent at any point during the study **for any reason**. This can happen at any time after consent and during follow up. In such an event no additional data will be collected from the patient and there will be no follow up. The study doctor will ascertain whether the patient wishes the withdrawal of consent to apply retrospectively to the withdrawal (i.e. can we use data already collected?). The outcome of any and all discussions regarding the withdrawal of consent will be documented in the medical notes and case report form.
- A patient's condition deteriorates due to heart failure or another pathology to the extent that they are expected to die within the next 24 to 48 hours.
- The study doctors deems the risk of continuation due to serious drug reactions or adverse events is too great to the patient. This will be fully discussed with the patient and the content and outcome of all discussions will be documented in the medical notes and CRF.
  - Worsening symptoms of heart failure\*
  - Hyponatraemia (<135 mmol/L)
    - Asymptomatic\*
      - Severe (<130 mmol/L)\*

    - Symptomatic (confusion, drowsiness, nausea or vomiting)\*\*
  - Hypotension
    - Asymptomatic\*
    - Symptomatic with no sequelae\*
    - Symptomatic with significant sequelae i.e. fall due to postural hypotension\*\*
  - o Hyperchloraemia
    - Mild 107 110 mmol/L\*
    - Severe >110mmol/L\*\*
  - Worsening renal function
    - >30% increase in serum creatinine from admission. \*
    - >50% increase in serum creatinine from admission.\*
    - >100% increase in serum creatinine from admission.\*\*
  - Side effects of acetazolamide: haemorrhage, ataxia, depression, diarrhoea, dizziness, fatigue, flushing, irritability, headache, loss of appetite, nausea, vomiting, taste disturbance, paraesthesia,
    - Tolerable to the patient.\*
    - Intolerable to the patient.\*\*

\* - Clinically relevant safety endpoint that would not automatically lead to the discontinuation of the study drug. Withdrawal would be at patient's request or the study doctor's discretion if the risk of continuation was deemed too high.

\*\* - Occurrence would lead to withdrawal from the study if it occurred in the acetazolamide arm

We will attempt to replace patients that withdraw from the trial prior to completing day 4 assessments. The reason(s) for withdrawal will be carefully monitored for trends in patient opinions of participation in the study, adverse drug reactions or adverse events.

